2.5.3 Handling of missing values/censoring/discontinuations

Missing values are replaced by the last available value. Post-baseline values are carried forward but no baseline values.

An analysis without replacing the missing data is performed as sensitivity analysis.

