6.6.4 Study completion, post-study treatment and early study termination

The study will be considered completed for an individual patient when he/she completes visit 7.

After premature withdrawal Visit 7 should be scheduled as soon as possible.

The study can be terminated for reasons stipulated in the study contract. Should this be necessary, the patients should be contacted and scheduled for their end of study assessments as described in Section 7. Novartis will be responsible for informing IRBs and/or IECs of the early termination of the study.

7 Visit schedule and assessments

Table 7-1 lists all of the assessments and indicates with an “X” the visits when they are performed and recorded in the clinical database.

Patients who prematurely withdraw from the study for any reason, should be scheduled for a final visit, at which time all of the assessments listed for the final visit will be performed.

Patients should be seen for all visits on the designated day with an allowed visit window of +/- 14 days for visits 3 to 7.

In addition to the scheduled visits, patients may have unscheduled visits following an infection, relapse or for other reasons as indicated in the protocol. All information should be collected.

Medications used to treat MS may include glatiramer acetate (Copaxone[®]), interferon β -1a i.m. (Avonex[®]), interferon β -1a s.c. (Rebif[®]), interferon β -1b (Betaseron[®]/Betaferon[®]), natalizumab (Tysabri[®]), azathioprine, methotrexate or any other medications used as MS-disease-modifying agents. Patients are not allowed to take these medications during the study. Other medications to treat MS-related symptoms should be recorded in the Concomitant Medication CRF. MS history should be supplemented by review of the patient's medical chart and/or by documented dialog with the patient's referring physician.

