1.1 Study design

This is a multi-center, open-label study in RRMS patients treated with fingolimod. After signing the informed consent, patients will enter a Screening Phase (day -28 to day 0) before starting the study at Baseline (visit 2/day 0), followed by a 36-month longitudinal data collection phase. Visits are performed at month 3 (visit 3), month 6 (visit 4), month 12 (visit 5), month 24 (visit 6), and month 36 (visit 7). Eligibility will be determined at Screening. OCT and other assessments will be performed according to the schedule in Table 7-1 of the Clinical Study Protocol (CSP).

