2.2 Analysis sets

The analysis sets were defined in section 10 of the Clinical Study Protocol (CSP):

The Safety Set (SAF) consists of all patients treated with investigational drug (fingolimod) for whom safety information was collected. Of note, the statement that a patient has had no adverse events also constitutes a safety assessment.

The Full Analysis Set (FAS) consists of all patients treated with investigational drug (fingolimod) for whom data was collected and who have at least one post-baseline efficacy assessment. This is analogous to the ITT population.

The Per Protocol Population consists of all patients from the FAS population, for whom no major protocol violations are reported. All reported protocol violations will be classified as minor or major in a data review meeting prior to data base lock.

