2.5 Analysis of the primary objective

2.5.1 Primary endpoint

The primary endpoint is the change, i.e. difference, in mean RNFLT from baseline to month 36 (or last values in case of missing data) in the full analysis set. Mean RNFLT is the average of valid measurements of the right and left eye.

Sensitivity analyses are performed with the Per-Protocol Set (PPS) and for the relative change assessed by the M36/BL.

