2.7.3 Handling of missing values/censoring/discontinuations

Missing values are replaced by the last available value. According to the definition of FAS (at least one post-baseline value of the primary parameter is required) all patients have a value after baseline.

In contrast to the primary parameter no sensitivity analysis without replacing the missing data is performed.

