5.4 Rule of exclusion criteria of analysis sets

Table 1 *Protocol deviations that cause subjects to be excluded*

Deviation ID	Description of Deviation	Exclusion in Analyses
I1	Informed consent not obtained	Excluded from all analyses
I3	Subject aged < 18	Excluded from PP analysis
I4	Subject not diagnosed with RRMS	Excluded from all efficacy analyses
I5	Subject with EDDS > 6.0 at baseline visit	Exclude from PP analysis
I6	Subject not stable on Fingolimod for at least 28 days and at most 4 months prior to screening	Excluded from PP analysis
I7	Evidence of acute relapse within 30 days prior to baseline visit	Excluded from PP analysis
E1	Forbidden concomitant medication	Case by case review: excluded from PP analysis
E3	Subject is suffering from a cardiovascular condition	Case by case review: excluded from PP analysis (if relevant for primary parameter)
E4	Subject suffering from severe respiratory disease	Case by case review: excluded from PP analysis
E5	Subjects with history of specific MRI findings	Excluded from PP analysis
E7	Subject with a history of a malignancy of any organ system within the past 5 years	Excluded from PP analysis (Exception: localized basal cell carcinoma of the skin)
E8	Use of other investigational drug/therapy within 90 days or 5 half-lives of screening	Case by case review: excluded from PP analysis
E9	Pregnant or nursing women	Excluded from PP analysis
E10	Subject with any ophthalmologic reason for RNFL pathology other than MS	Case by case review: excluded from PP analysis
E11	History or active severe myopia	Case by case review: excluded from PP analysis
E12	Acute optic neuritis within the last 6 months prior to screening	Excluded from PP analysis

Deviation ID	Description of Deviation	Exclusion in Analyses
E13	Evidence of advanced diabetic retinopathy	Excluded from PP analysis
E14	Presence of retinal conditions	Case by case review: excluded from PP analysis
E15	Concomitant use of drugs that may directly affect retinal structure and function	Case by case review: excluded from PP analysis
S1	Treatment regime changed	Excluded from PP analysis
O1	Baseline OCT measurements not performed	Excluded from PP analysis
O3	Difference between visit 7 and baseline \leq 1035 days	Excluded from PP analysis

Table 2 Subject Classification

Analysis Set	PD ID that cause subjects to be excluded	Non-PD criteria that cause subjects to be excluded

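### Last-value-carried-forward is the primary handling of a missing month-36 RNFLT, so a month-3 change can count as the 36-month change and loss is understated if thinning continues

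*SAP*

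**What the plan says.** SAP 2.5.1 defines the endpoint: "The primary endpoint is the change, i.e. difference, in mean RNFLT from baseline to month 36 (or last values in case of missing data", analysed in the FAS. SAP 2.5.3 gives the rule: "Missing values are replaced by the last available value. Post-baseline values are carried forward but no baseline values". The SAP's definition of the last value until a visit applies the same rule to invalid measurements and sets no minimum follow-up time for the carried scan.

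Protocol 7.3 schedules OCT at baseline and at visits 3 to 7. SAP 1.1 places visit 3 at month 3 and the last two visits at "month 24 (visit 6), and month 36 (visit 7". The FAS takes patients "who have at least one post-baseline efficacy assessment" (SAP 2.2).

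Two checks are planned for the primary endpoint. SAP 2.5.3 states: "An analysis without replacing the missing data is performed as sensitivity analysis". A per-protocol (PPS) analysis excludes patients whose treatment regime changed (deviation S1). It also excludes those for whom O3 applies (SAP 5.4): "Difference between visit 7 and baseline" of 1035 days or less. For the secondary OCT endpoints SAP 2.7.3 says: "In contrast to the primary parameter no sensitivity analysis without replacing the missing data is performed".

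Protocol 10.4.3 holds that imputation is unnecessary because every FAS patient has a post-baseline OCT. SAP section 4, which lists departures from the Protocol, mentions only the ganglion cell layer measure.

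**The concern.** Carrying a value forward assumes that thinning stops at the last scan. Protocol section 1 says the opposite of MS eyes in general: the limited longitudinal data show thinning progressing over time. Under that premise every replaced value is too close to zero, and the mean 36-month loss under fingolimod looks smaller than it is. The study has one arm and tests no hypothesis, so this estimate is its main product.

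The planned checks leave three gaps.

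- The unreplaced analysis is unbiased only if missingness is unrelated to thinning. If faster-thinning patients leave, it errs in the same direction as carry-forward, and agreement between the two would reassure falsely.
- Protocol 6.6.4 says "After premature withdrawal Visit 7 should be scheduled as soon as possible", and SAP 1.1 equates visit 7 with month 36. An early exit scan in the FAS may therefore count as an observed month-36 value even without replacement. In the text available only O3 deals with this, and only for the PPS. A windowing rule may exist in SAP text not available here.
- As worded, O3 does not clearly exclude a patient who has no visit 7 at all.

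**Working it through.** There is no figure in the plan to reproduce. The sample of about 100 is not derived from a power calculation, and neither document gives a dropout rate, thinning rate or SD.

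**Inputs from the documents:** OCT at months 0, 3, 6, 12, 24 and 36; about 100 patients; the O3 limit of 1035 days (1035/30.44 = 34.0 months).

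**Assumptions:** share *p* of month-36 scans missing, 10 to 40%; the shape of mean thinning; the timing of last scans.

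**Step 1: what one carried scan captures.** Under linear thinning a scan at month *t* holds *t*/36 of the 36-month change: 3/36 = 8.3%, 6/36 = 16.7%, 12/36 = 33.3%, 24/36 = 66.7%.

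**Step 2: effect on the mean.** With mean last-scan time *m*, the fraction of true loss recovered is (1 − *p*) + *p*·*m*/36. Even spread over the four visits gives *m* = (3 + 6 + 12 + 24)/4 = 11.25. An exit OCT midway between visits gives *m* = (4.5 + 9 + 18 + 30)/4 = 15.375. For *p* = 0.2 and *m* = 11.25: 0.8 + 0.2 × 11.25/36 = 0.8625, so an assumed true loss of 3.0 µm is reported as 2.59 µm.

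**Step 3: front-loaded loss.** Replace *t*/36 by (1 − e^(−t/6))/(1 − e^(−6)), an exponential with a 6-month time constant, using the four scheduled visits.

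**Step 4: dropouts thin twice as fast as completers.** Carry-forward recovers [(1 − *p*)·36 + 2*p*·11.25]/[(1 + *p*)·36]. The unreplaced (observed-case) analysis recovers 1/(1 + *p*).

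| Fraction of true loss recovered | 10% missing | 20% | 30% | 40% |
|---|---|---|---|---|
| Carry-forward, linear, last scheduled scan | 0.931 | 0.863 | 0.794 | 0.725 |
| Carry-forward, linear, exit scan midway | 0.943 | 0.885 | 0.828 | 0.771 |
| Carry-forward, front-loaded | 0.972 | 0.944 | 0.916 | 0.888 |
| Carry-forward, dropouts twice as fast | 0.875 | 0.771 | 0.683 | 0.607 |
| Observed-case, dropouts twice as fast | 0.909 | 0.833 | 0.769 | 0.714 |

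**Step 5: simulation.** 2000 runs, n = 100, the scheduled OCT times, mean slope −1 µm/year (true 36-month change −3.00 µm), slope SD 0.7 µm/year, error SD 1 µm, 30% missing at month 36. The mixed model had the correct linear mean and known variance components.

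| Dropout mechanism | Carry-forward | Observed-case | Mixed model |
|---|---|---|---|
| Unrelated to loss | −2.36 | −3.00 | −3.00 |
| Odds × 1.65 per µm of observed loss | −2.48 | −2.59 | −3.00 |

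In the second row carry-forward and observed-case differ by 0.11 µm, yet they miss the truth by 0.52 and 0.41 µm.

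**The case against.** **The SAP already plans checks.** This stands in part. If dropout is unrelated to thinning, the unreplaced analysis exposes the bias. But it is not the headline, it fails under informative dropout, and it does not exist for the secondary OCT endpoints.

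**The study is descriptive.** No type I error is at stake, and summary statistics are planned at each time point. That limits the severity. It does not excuse a biased estimate in a study whose purpose is estimation.

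**The size is assumed, and an even spread over four unevenly spaced visits puts dropout early.** This is fair. With dropout uniform over months 3 to 36, the mean last scheduled scan is (3×3 + 3×6 + 6×6 + 12×12 + 12×24 − 3×6)/33 = 477/33 = 14.5 months, and carry-forward recovers 94, 88, 82 and 76% at 10 to 40% missing. With an exit scan (mean 19.5 months) it recovers 95, 91, 86 and 82%. Protocol section 7 asks for all final-visit assessments at withdrawal, so the exit-scan figures fit patients who attend that visit. Protocol 10.7 also notes that there are no thinning data under fingolimod.

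**The simulation suits the mixed model.** This is also fair: its data meet that model's assumptions. When dropout instead depends on each patient's true slope (log-odds 0.5 per µm of 36-month loss, 30% missing, 600 runs), the results are −2.02 for carry-forward, −2.40 for observed-case and −2.55 for the mixed model, against −3.00. The remedy is then biased too, but least so.

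**The points on an early or absent visit 7 depend on incomplete text.** They are matters to clarify, and the main conclusion does not need them.

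**Conclusion.** The concern holds and should be fixed. By its stated rules the SAP lets a change measured at month 3 enter the mean 36-month change. Understatement requires two conditions: some month-36 scans missing, and thinning that continues after the last scan. If either fails, the bias from this source is zero.

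Under linear thinning with dropout unrelated to loss, the shortfall is about 5 to 7% at 10% missing and 18 to 28% at 40%, depending on when last scans occur. It is smaller if loss is front-loaded and larger if dropouts thin faster. These percentages do not depend on the thinning rate, but the missing share and the timing are assumptions. Confidence is high about the rule and the direction of the bias; the actual size cannot be fixed from the documents.

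**What to change.** - **Primary analysis.** Use a likelihood-based repeated-measures model on all OCT values, including early-exit scans, each at its actual time since baseline, so that an early visit 7 is not labelled month 36. Include a patient random intercept and slope, and a mean that can bend, for example piecewise linear with knots at months 12 and 24.
- **Reporting.** Give the month-36 change with a 95% CI, the annualised rate, and the month 12–24 and 24–36 changes named in Protocol 10.4.2. This also serves the rate and pattern of change in Protocol 10.4.1.
- **Secondary OCT endpoints.** Apply the same model to quadrant RNFLT, macular volume and the ganglion cell–inner plexiform measure.
- **Sensitivity analyses.** Keep carry-forward and observed-case. State how each treats an early and an absent visit 7, and report the number and timing of carried values.
- **Documentation.** Record the change in SAP section 4, together with the departure from Protocol 10.4.3.

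The cost is SAP wording and standard mixed-model code, with no new visits or data. The model relies on missing-at-random and on its mean form, and the estimated loss may look less favourable. A smaller step is to give the unreplaced analysis equal standing and extend it to the secondary endpoints. That would show the carry-forward bias when dropout is unrelated to thinning, but not when it is related.

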2.5.4 Supportive analyses

A comparison for eyes with versus without optic neuritis is done by a mixed model including the subject as random factor. LSMMeans for RNFLT in eyes with versus without optic neuritis are displayed as well as the difference including p-value.

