10.5 Analysis of secondary [REDACTED] objectives

10.5.1 Secondary [REDACTED] outcomes

Secondary endpoints like changes in quadrant RNFLT, changes in total macular volume (TMV), and changes in ganglion cell layer thickness (GCLT) from baseline to months 12, 24, and 36 will be evaluated with a paired t-test or Wilcoxon signed-rank test, as appropriate.

Changes in OCT parameters between eyes with and without history of optic neuritis will be evaluated with a paired t-test or Wilcoxon signed-rank test, as appropriate.

[REDACTED]

Additionally, means, standard deviations, median, minimum and maximum will be presented for each visit, as will be the change from baseline. These descriptive statistics will also be presented for the primary endpoint.

For all other [REDACTED] endpoints summary statistics will be presented. Summary statistics will include n (number of observations), mean, standard deviation, median, minimum and maximum values at each visit, as well as the change.

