2.7.2 Statistical hypothesis, model, and method of analysis

No hypothesis is to be tested. P-values are displayed as descriptive measures.

Analysis is similar to the primary endpoint. All analyses are done with the FAS only.

Correlations in the change from baseline to month 12, month 24 and month 36 are presented by the Pearson correlation coefficient or Spearman Rank correlation coefficient, depending on distribution of data. Normality was graphically investigated..

Correlations are displayed graphically by scatter plots. Here, only changes from baseline to last value until Month 36 are displayed.

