2.14 Interim analysis

Not applicable.

3 Sample size calculation

Published data varies widely as to the average thinning of RNFL in MS patients and no data is available on patients treated with Fingolimod. As this is an explorative study to get a better understanding of RNFL thinning in RRMS treated with Fingolimod we will take a representative sample of approximately 100 patients with RRMS who are stable on Fingolimod

4 Change to protocol specified analyses

[figure not shown]
The change in ganglion cell layer thickness (GCLT) was defined as secondary endpoint, but OCT measured the ganglion cell inner plexiform layer (GCIP). This was done because both layers are not clearly separable by OCT. The volume of GCIP is declared as usual parameter.

5 Appendix

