5.3.2 Key secondary analysis

The SAS syntax for mixed model to compare RNFLT in eyes with versus without optic neuritis is:

```
proc mixed data=test5;
```

```
class patno opt_neur ;
model rnflt = opt_neur;
random patno;
lsmeans krank / tdiff pdiff;
run;
```

RNTFL ist the difference from BL to last value until M36. Here no average over both eyes is calculated, but each measurement is included in the dataset and flagged in OPT_NEUR if the respective eye was affected by optic neuritis history.

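### The SAP's optic-neuritis eye comparison mixes within-patient and between-patient differences, whereas the protocol plans a paired test; the switch is not listed in the visible part of SAP section 4

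*SAP*

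**What the plan says.** Comparing OCT changes between eyes with and without optic-neuritis history is a secondary objective (Protocol 3.2; SAP 1.2). The two documents analyse it differently.

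- Protocol 10.5.1: "Changes in OCT parameters between eyes with and without history of optic neuritis will be evaluated with a paired t-test", with a signed-rank test as the alternative. The pair is not defined.
- SAP 2.5.4: "A comparison for eyes with versus without optic neuritis is done by a mixed model including the subject as random factor". LS-means for the two kinds of eye "are displayed as well as the difference including p-value".
- SAP 5.3.2 gives the code. The fixed part is "model rnflt = opt_neur", with a random patient effect. The response is the change from baseline to the last value until month 36. On the data, it says: "Here no average over both eyes is calculated, but each measurement is included in the dataset".
- SAP 5.3.2 requests LS-means for `krank`, which appears in neither the CLASS nor the MODEL statement.
- SAP section 4, on changes to protocol-specified analyses, visibly lists one item, which begins: "The change in ganglion cell layer thickness (GCLT) was defined as secondary endpoint". It goes on to explain that GCIP was measured instead.
- SAP 2.7.2 states that no hypothesis is tested and that "P-values are displayed as descriptive measures".

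**The concern.** In a patient with one affected eye, the optic-neuritis flag differs between that patient's two eyes. In a patient with no affected eye or two, it is the same in both, so it varies only between patients. Protocol 5.1 excludes only acute optic neuritis in the six months before screening, so all three kinds of patient can enrol.

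A random intercept with no patient-level optic-neuritis term treats the patient effect as unrelated to the flag. It therefore pools two contrasts: affected versus fellow eye, and patients with more versus fewer affected eyes. A reader of the displayed difference could not tell whether affected eyes thin differently or whether patients who have had optic neuritis thin faster in both eyes. A paired test on affected and fellow eyes responds only to the first.

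**Working it through.** **Inputs.** The documents give about 100 patients, not derived from a calculation (Protocol 10.7), the eligibility rule and the model. They give no SD, inter-eye correlation, optic-neuritis mix, effect or alpha for this comparison, so there is no stated figure to reproduce. Everything else below is an assumption:

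- both eyes measured in 100 patients, with the SD of an eye's change set to 1;
- inter-eye correlation ρ;
- n₁ patients with one affected eye, n₂ with two, n₀ with none;
- true affected-minus-fellow difference exactly 0;
- patients with any optic-neuritis history lose δ SD more in **both** eyes.

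**Formulas.** Let p be a patient's proportion of affected eyes (0, 0.5 or 1) and a = 1 for any history. Let S = Σ(p − p̄)² and C = Σ(a − ā)(p − p̄).

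- Within-patient information: W = n₁ / [2(1 − ρ)]
- Between-patient information: B = 2S / (1 + ρ)
- The SAP coefficient is the weighted mean of the two contrasts, with weights W and B. Its standard error is 1/√(W + B).
- Its bias for the within-patient contrast is [B/(W + B)] × δ × C/S.
- With p added as a covariate, the bias is 0 and the standard error is 1/√W.

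**Example 1:** n₁/n₂/n₀ = 40/10/50, ρ = 0.5, δ = 0.5.

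- p̄ = (40 × 0.5 + 10)/100 = 0.30
- S = 40 × 0.25 + 10 − 100 × 0.09 = 11
- C = 40 × 0.5 + 10 − 100 × 0.5 × 0.30 = 15
- W = 40/(2 × 0.5) = 40; B = 22/1.5 = 14.67; between-patient weight = 14.67/54.67 = 0.268
- Bias = 0.268 × 0.5 × 15/11 = 0.183 SD (simulation: 0.176)
- Standard error = 1/√54.67 = 0.135; bias/SE = 1.35. Against a critical value of 1.98, p < 0.05 in about Φ(1.35 − 1.98) ≈ 26% of trials (simulation: 24.9%; paired t-test: 4.9%).

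**Example 2:** 35/15/50, ρ = 0.5, δ = 0.5.

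- p̄ = 0.325; S = 8.75 + 15 − 10.5625 = 13.19; C = 32.5 − 16.25 = 16.25
- W = 35; B = 26.375/1.5 = 17.58
- Bias = (17.58/52.58) × 0.5 × 16.25/13.19 = 0.206 SD
- SE = 1/√52.58 = 0.138 for the SAP model and 1/√35 = 0.169 within patients, which is 23% larger.

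**Simulation of the SAP model.** REML fit, t-test on 99 df, 10,000 trials per setting; mixes n₁/n₂/n₀ of 30/5/65, 40/10/50 and 50/10/40. Entries are the share of trials with p < 0.05 when affected and fellow eyes change equally.

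| Patient-level shift δ | ρ = 0.2 | ρ = 0.5 | ρ = 0.8 |
|---|---|---|---|
| 0 | 4.9–5.2% | 4.7–4.9% | 4.9–5.2% |
| 0.25 SD | 13–16% | 9–11% | 6–7% |
| 0.5 SD | 37–45% | 20–26% | 10–12% |
| 1.0 SD | 80–91% | 50–65% | 20–25% |

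At δ = 0.5 SD the mean false difference runs from 0.055 SD (ρ = 0.8) to 0.324 SD (ρ = 0.2).

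A second simulation used n₁/n₂/n₀ of 35/15/50, 40/20/40 and 30/10/60, ρ from 0.3 to 0.7 and 4,000 runs per setting. It gave 4.6–5.6% with no shift, 9–20% at 0.3 SD, and 17–45% at 0.5 SD with a false difference of 0.11–0.30 SD.

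**After the change.** In the first simulation the paired t-test gives 4.6–5.5%, and the SAP model with p added gives 4.6–5.6%. In the second, the model with p added gives 4.4–5.6% with bias about 0.

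**The case against.** Five points can be made for the SAP.

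1. **The target is not stated as within-patient.** The objective speaks only of eyes with and without history, and Protocol 10.5.1 does not define the pair. This stands: within-patient pairing is the natural reading of a paired test, but it is an inference. An all-eyes mixed model is a legitimate way to use every patient while handling clustering. A reader might conclude that the SAP model is invalid. It is not; it answers a different, mixed question.

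2. **Nothing is being tested.** SAP 2.5.2 and 2.7.2 set no hypothesis, the model sits under supportive analyses, and Protocol 10.7 calls the study explorative. A reader might infer an inflated type I error. The documents set no error rate for this comparison, so that reading fails. The estimate can still mislead, because calling a p-value descriptive does not remove bias from the difference shown beside it.

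3. **The bias needs a patient-level shift.** This stands: with none, the SAP model stays at about 5%. A reader might take Protocol section 1 as evidence that patients with optic-neuritis history thin faster in both eyes. It does not say so. The correlations with brain atrophy and cognition come from cross-sectional work on thickness, not change, and the protocol says further studies of change are needed.

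4. **The within-patient contrast discards information.** It rests on patients with one affected eye and is less precise. This stands as a cost, and is a reason to keep both rows.

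5. **The change may be declared elsewhere.** Part of SAP section 4 is not shown, so the claim covers only what is visible.

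**Conclusion.** The mismatch is confirmed from the text: the protocol plans a paired test, the SAP uses a random-intercept model on all eyes with no patient-level optic-neuritis term, and the visible part of SAP section 4 does not list the change.

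The consequence is conditional. If patients with optic-neuritis history change more in both eyes, the displayed difference is biased for the within-patient contrast. A 0.5 SD shift gives a bias of roughly 0.1 to 0.3 SD and p < 0.05 in roughly 10 to 45% of trials, less as inter-eye correlation rises. The shift, mix and correlation are assumptions, so these sizes are illustrative.

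The effect is confined to a descriptive secondary comparison. It is worth correcting because the change is small and the current output cannot separate the two explanations.

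**What to change.** - In SAP 2.5.4 and 5.3.2, derive `on_prop`, the patient's proportion of affected eyes, from the eyes actually in the model, so that a patient with one valid eye is handled correctly. Enter it as a continuous covariate: `model rnflt = opt_neur on_prop; random patno;`.
- Report the OPT_NEUR coefficient from this model as the within-patient comparison implied by Protocol 10.5.1. Keep the present all-eyes model beside it, labelled as mixing within- and between-patient differences.
- Replace `krank` with `opt_neur` in the LSMEANS statement. As written, the code does not request the LS-means that SAP 2.5.4 promises.
- Add a line to SAP section 4 on the change from the paired test.

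**Cost:** one derived variable, one model term and one line of text. The within-patient standard error is about 12 to 36% larger than that of the present model under the second simulation's mixes with ρ from 0.3 to 0.7. All eyes stay in the dataset, but the within-patient row draws its information from patients with one affected eye.
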